We will screen for subjects at 3 main clinic areas: a. the medicine clinics at MEDVAMC and b. the cardiology clinics at MEDVAMC. c. the endocrinology clinics at MEDVAMC. Our research co-ordinators will review daily out patient visits at the clinics of the PI and his co-investigators and identify potential subjects to approach and discuss the study. In addition we will describe the study and its goals to various primary care providers and ask them to inform their patients about our study so that interested individuals can contact us. Then, the research co-ordinators will approach the subject and ask if they are interested in learning about the study. To those interested a description of the study, its requirements, and details related to subject participation, visits and risks will be discussed in detail. They will be provided with the consent form and have an opportunity to review the same. The consent form will also be discussed by the study co-ordinator with the subject. Any questions that may arise will be answered by the co-ordinators. Then the subject will, if interested, be asked to come to the pre-randomization visit when we will answer any other questions they have. Then we will request the subject to sign the consent form.

Then their blood will be sent to the Atherosclerosis laboratory at BCM where the high sensitivity troponin assay will be done. We anticipate that these lab assays will be done on a weekly or bi-weekly (once in 2 weeks) basis. Then, if the patient qualifies based on this we will randomize them. The biomarkers to see if the subject qualifies for the study and also to study the effect of therapy (namely troponin T and NT proBNP) will have to be done at the Atherosclerosis labs at BCM as troponin assay we use (a high sensitivity assay) is currently only research and not available clinically.

Similarly other future markers done as research may need to be done at Baylor. Samples sent to BCM will only have a research ID and study week. There will be no HIPAA identifiers. For example, subject #1,s coding on the blood sample may read VAHFP0001W1 where VAHFP is the general study ID, 0001 is the subject ID and W1 states that it is the first sample. A code for this to identify the subject will be maintained at MEDVAMC under password protection. Please note that we may change the general study ID (i.e. VAHFP) to a similar alternative if other similar stems already exist to avoid confusion.

Are foreign language consent forms required for this protocol?

No

J3. Privacy and Intrusiveness

Will the research involve observation or intrusion in situations where the subjects would normally have an expectation of privacy?

No

J4. Children

Will children be enrolled in the research?

No

J5. Neonates

Will non-viable neonates or neonates of uncertain viability be involved in research?

No

J6. Consent Capacity - Adults who lack capacity

Will Adult subjects who lack the capacity to give informed consent be enrolled in the research?

No

J7. Prisoners

Will Prisoners be enrolled in the research?

No

Section K: Research Related Health Information and Confidentiality

Will research data include identifiable subject information? Yes

Information from health records such as diagnoses, progress notes, medications, lab or radiology findings, etc.

Yes

Specific information concerning alcohol abuse:

Yes

Specific information concerning drug abuse:

Yes

Specific information concerning sickle cell anemia:

No

Specific information concerning HIV:

No

Specific information concerning psychiatry notes:

No

Demographic information (name, D.O.B., age, gender, race, etc.):

Yes

Full Social Security #:

Yes

Partial Social Security # (Last four digits):

Yes

Billing or financial records:

No

Photographs, videotapes, and/or audiotapes of you:

No

Other:

No

At what institution will the physical research data be kept?

Physical research data will be stored and locked in the research/PI offices at MEDVAMC. Physical Data will be kept in locked cabinets which only the PI/ research staff have access to via key

How will such physical research data be secured?

Sensitive paper data will be stored and locked in the research/PI offices in the section of Cardiology at MEDVAMC

At what institution will the electronic research data be kept?

The electronic data will be stored at MEDVAMC and on web based platform hosted by BCM. Such electronic research data will be secured via BCM IT Services- provided secured network storage of electronic research data (Non-Portable devices only):

Yes

Such electronic research data will be secured via

Other:

Yes, (describe below):

Data will be kept secure in password protected files behind a secure VA network server. Strain analysis and pulse wave analysis are done through independent software on laptops. These laptops will be secured in locked cabinets in the PI's office or research office.

Will there be anyone besides the PI, the study staff, the IRB and the sponsor, who will have access to identifiable research data?

Yes, identify the classes of the persons:

People who ensure quality from the institutions where the research is being done, federal and other regulatory agencies will have access to all of the research data.

Please describe the methods of transmission of any research data (including PHI, sensitive, and non-sensitive data) to sponsors and/or collaborators.

All data entered into the eCRFs are transmitted over secure encrypted channels to the ICTR database server.

For statistical analysis- data will be transferred. Data will be transferred through email for statistical analysis and will be as EXCEL spreadsheets (echocardiogram data analyses, pulse wave data analysis, biomarker data as obtained from Baylor College of Medicine, subject baseline and follow up characteristics including labs, AE/ SAE).

Only subject research ID (example HB 01, HB 02 along with possibly a suffix A or B to identify randomization visit vs. end of study information) will be there as an identifier. No specific patient/ subject related ID (example date of birth, social security number) will be included in the data transferred

A copy of the data will be sent to the MEDVAMC Privacy Officer to confirm no identifiers are present before transferring to sponsors and/or collaborators.

Will you obtain a Certificate of Confidentiality for this study?

No

Please further discuss any potential confidentiality issues related to this study.

Research records, including identifiers will be destroyed 6 years after cutoff (at the end of the fiscal year) after completion of the research project, but may be retained longer if required by other federal regulations or sponsor archive requirement.

The purpose of collecting information covered under 38 U.S.C. 7332 is to conduct scientific research and no personnel involved in this study will identify, directly or indirectly, any individual patient or subject in any report of such research. It is understood by the PI that data will not be used or shared with others outside the scope of the research study as documented in the protocol approved by the IRB and MEDVAMC R&D committee. Removal of access to research study data will be accomplished for all study personnel when they are no longer part of the research team.

An Accounting of Disclosure (AOD), will be created and maintained for any disclosure of individually identifiable information (III), outside the VA. The manual spreadsheet will include the data of the disclosure, nature or description of the III disclosed, purpose of each disclosure and the name and address of the person or agency to which the disclosure was made.

Cost/Payment

Delineate clinical procedures from research procedures. Will subject's insurance (or subject) be responsible for research related costs? If so state for which items subject's insurance (or subject) will be responsible (surgery, device, drugs, etc). If appropriate, discuss the availability of financial counseling.

There will be no costs to the subject. This study is sponsored through a VA MERIT grant award and subjects will be recruited exclusively at the MEDVAMC. The echocardiogram, measures of pulse wave velocity, drug (spironolactone/ carvedilol), measurement of troponin and BNP tests are all research

If subjects will be paid (money, gift certificates, coupons, etc.) to participate in this research project, please note the total dollar amount (or dollar value amount) and distribution plan (one payment, pro-rated payment, paid upon completion, etc) of the payment.

Dollar Amount:

125

Distribution Plan:

There are 5 visits. For each visit we will provide the subject with \$25 to defray the expenses of travel and food. The money will be paid by cash after the subject has completed the visit

Genetics

How would you classify your genetic study?

Discuss the potential for psychological, social, and/or physical harm subsequent to participation in this research. Please discuss, considering the following areas: risks to privacy, confidentiality, insurability, employability, immigration status, paternity status, educational opportunities, or social stigma.

Will subjects be offered any type of genetic education or counseling, and if so, who will provide the education or counseling and under what conditions will it be provided? If there is the possibility that a family's pedigree will be presented or published, please describe how you will protect family member's confidentiality?

Sample Collection

SAMPLE: Blood

What is the purpose of the sample collection?

The purpose of sample collection is 1. Biomarker assay which will qualify the patient for the study and is required to see the effect of therapy 2. Storage of blood for future possible biomarker studies. The biomarkers to see if the subject qualifies for the study and also to study the effect of therapy (namely troponin T and NT proBNP) will have to be done at the Atherosclerosis labs at BCM as troponin assay we use (a high sensitivity

assay) is currently only research and not available clinically. Similarly other future markers done as research may need to be done at Baylor. Samples sent to BCM will only have a research ID and study week. There will be no HIPAA identifiers. For example, subject #1,s coding on the blood sample may read VAHFP0001W1 where VAHFP is the general study ID, 0001 is the subject ID and W1 states that it is the first sample. A code for this to identify the subject will be maintained at MEDVAMC under password protection. Please note that we may change the general study ID (i.e. VAHFP) to a similar alternative if other similar stems already exist to avoid confusion.

For blood draws, specify the amount drawn, in teaspoons, at each visit and across the course of the subjects entire participation time.

Blood will be collected at baseline, after starting spironolactone, any titration of dose, at 6 months, 12 months and study end. At baseline, 12 months and study end we will collect 8 teaspoons while after starting spironolactone/ titration of dose/ 6 months we will draw adequate blood to check a basic metabolic panel (~ 2 teaspoons). In all this makes the total blood collection during the study period to be 24-30 teaspoons

Is there the possibility that cell lines will be developed with this sample? No

Sample will be obtained from:

Clinical Labs, Other: Research co-ordinator

Will the sample be stripped of identifiers?

No

If sample will be released outside the hospital:

Will sample be released to anyone not listed as an investigator on the protocol? Will the information be identifiable, coded or de-identified?

There are no plans at this time to release the samples to investigators not on the protocol

Will sample material be sold or transferred to any third parties? Will the information be de-identified?

No sample will be sold

If sample will be banked for future use:

Where will the sample be banked and for how long?

The samples will be stored in the freezer farm at the VA research buildings and will be stored for the duration of the study. Additional biomarker testing may be done (depending on obtaining funding) by the research team involved in this study

Does the banking institution have an approved policy for the distribution of samples?
NA: there will be NO distribution of samples. Future research will be done only by this study team

If the entire sample will NOT be used during the course of this research study:

Will the remaining tissue be discarded? If not what will be done with the remaining sample after study completion and how long will the sample be kept?

The samples will be stored for the duration of the study and the extra sample (if any) will be discarded

Will samples be made available to the research subject (or his/her medical doctor) for other testing?

No

If a subject withdraws from the study:

Will subject have the option to get the remaining portion of their sample back?

No

Will samples be destroyed? If not, will they be kept anonymously? What will happen to the sample if the subject revokes authorization?

If the subjects withdraws/ revokes authorization his/ her sample will not be used and will be discarded

Will data obtained from their sample be deleted? What will happen to the sample if the subject revokes authorization?

If the subject has not completed the study the sample will be deleted for analysis. If the subject completed the study and revokes authorization we will not use the data for analysis

Will study data or test results be recorded in the subject's medical records?

No

Will results of specific tests and/or results of the overall study be revealed to the research subject and or his/her doctor?

The results of the potassium will be available on the patients chart (CPRS). Other research specific data/ biomarker will not be available to other subjects

Please identify all third parties, including the subject's physician, to receive the test results.

Anyone with authorized access to the patients chart on CPRS (the electronic medical record) will be able to review the potassium result when spironolactone is started/ dose changed and at 6, 12 and 18 months. No other data will be made available to the subjects physician

SAMPLE: Urine

What is the purpose of the sample collection?

Urine will be collected for a pregnancy test only in women of child bearing potential.

For blood draws, specify the amount drawn, in teaspoons, at each visit and across the course of the subjects entire participation time.

Not applicable

Is there the possibility that cell lines will be developed with this sample?No

Sample will be obtained from:

Clinical Labs

Will the sample be stripped of identifiers?

No

If sample will be released outside the hospital:

Will sample be released to anyone not listed as an investigator on the protocol? Will the information be identifiable, coded or de-identified?

The sample will not be released

Will sample material be sold or transferred to any third parties? Will the information be de-identified?

The sample will not be sold or transferred to anyone else

If sample will be banked for future use:

Where will the sample be banked and for how long?

The urine sample will not be banked

Does the banking institution have an approved policy for the distribution of samples?

Not applicable

If the entire sample will NOT be used during the course of this research study:

Will the remaining tissue be discarded? If not what will be done with the remaining sample after study completion and how long will the sample be kept?

The remaining sample will be discarded per VA lab policies

Will samples be made available to the research subject (or his/her medical doctor) for other testing?

No

If a subject withdraws from the study:

Will subject have the option to get the remaining portion of their sample back?

No

Will samples be destroyed? If not, will they be kept anonymously? What will happen to the sample if the subject revokes authorization?

Samples will be discarded immediately after the urine pregnancy test is completed as per VA lab policies (as with any other clinical sample)

Will data obtained from their sample be deleted? What will happen to the sample if the subject revokes authorization?

The results of the test will be part of the medical record in CPRS and will not be deleted

Will study data or test results be recorded in the subject's medical records?

Yes

Will results of specific tests and/or results of the overall study be revealed to the research subject and or his/her doctor?

The urine pregnancy test result will be discussed with the patient and since available in the medical record can be accessed by the patients physicians

Please identify all third parties, including the subject's physician, to receive the test results.

The test results will be available to anyone who accesses the patients medical records

Drug Studies

Does the research involve the use of ANY drug* or biologic? (*A drug is defined as any substance that is used to elicit a pharmacologic or physiologic response whether it is for treatment or diagnostic purposes)

Yes

Does the research involve the use of ANY gene transfer agent for human gene transfer research?

No

O1. Current Drugs

Drug : carvedilol

Drug : spironolactone

Is this study placebo-controlled?

No

Will the research involve a radioactive drug?

No

Device Studies

Does this research study involve the use of ANY device?

No

Advertisements

None

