1. Age greater than 40 years 2. One of the following in order to establish Stage A HF a. Hypertension b. Diabetes mellitus (controlled: defined as hemoglobin A1c less than 9%) c. Obesity (defined as BMI greater than 30 kg/m²) d. Metabolic syndrome (using the National Cholesterol Education Panel definition) e. Left ventricular hypertrophy (by ECG) f. Coronary or cerebrovascular arterial disease 3. Troponin T measured by the high sensitivity assay of greater than 5 ng/L 4. Systolic BP 120-155 mmHg at PCP visit and prerandomization visit (i.e., 2 separate confirmations of the same). If there is discordance between the PCP visit and pre-randomization we will use one of the following methods as the tie breaker:

- 1) Take an average of the 3 most recent BP measurements (within the past 6 months) in the subjects electronic medical record
- 2) Take a 5 day average of home BP measurements recorded by the subject.
- 3) Bring patient back to recheck their BP.

Not orthostatic with measurements (defined as a fall in systolic BP greater than 20 mmHg when subjects assumes an upright position). Note: If subjects systolic blood pressure is greater than 155 mmHg on date of randomization we will still include him/her if he/ she meets the above blood pressure criteria.

5. Estimated 10-yr HF risk (based on ARIC HF Lab model) greater than 5% 6. Provides informed consent

Exclusion Criteria:

On the other hand, the exclusion criteria focus on individuals in whom the end point (echocardiogram based measures) will be difficult to ascertain (irregular rhythm, COPD, radiation to the neck/neck) or who have other major comorbidities

1. Current atrial fibrillation 2. History of chest/ neck radiation 3. High-risk chronic obstructive pulmonary disease (COPD) (GOLD classification 3-4 with greater than equal to 2 COPD exacerbations in the last 12 months) 4. Known allergy to carvedilol or spironolactone 5. Renal insufficiency with eGFR less than 50 ml/min 6. Serum potassium greater than 5 meq/L 7. Current use of carvedilol, spironolactone, any other

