beta-blockers or aldosterone antagonists 8. Signs of clinical HF on initial examination (pulmonary rales/crackles, elevated jugular venous pulse with S3/S4 on auscultation) 9. Left ventricular ejection fraction <50% by echo 10. Moderate or greater valve stenosis or regurgitation 11. Hypertrophic cardiomyopathy 12. Exposure to known cardiotoxic chemotherapy 13. Poor echo image quality 14. Right ventricular dysfunction more than mild 15. Any valvular dysfunction that is more than mild 16. Any life threatening disease expected to result in death within the next 2 years 17. Active severe liver disease (evaluated at Visit 1): cirrhosis, active hepatitis, ALT or AST greater than 3 x ULN, or biliary obstruction with hyperbilirubinemia (total bilirubin greater than 2 x ULN). 18. Participation in another clinical trial involving an investigational agent within 90 days prior to randomization 19. Any condition or therapy which, in the opinion of the investigator, might pose a risk to the patient or make participation in the study not in the patients best interest 20. Drug or alcohol abuse within the past 6 months, and unable unwilling to abstain from drug abuse and excessive alcohol consumption during the study. Excessive alcohol consumption is on average greater than 2 units of alcohol per day. A unit of alcohol is defined as a 12-ounce (350 mL) beer, 5-ounce (150 mL) wine, or 1.5-ounce (45 mL) of 80-proof alcohol for drinks. 21. Mental/psychological impairment or any other reason to expect patient difficulty in complying with the requirements of the study. 22. Any immunosuppressed condition where intercurrent illnesses may affect interpretation of study results 23. Pregnant women or any woman planning a pregnancy during the study period 24. Not meeting any of the inclusion criteria

Procedure

As per VA regulations, the health record of the subject will be flagged to indicate that he/she is participating in a research study.

Prerandomization Visit: During this visit, inclusion and exclusion criteria will be reviewed to ensure that subject eligibility. The informed consent document will be reviewed with those eligible for the study and willing to participate. We will answer all their questions and then if the subject is still interested have them sign the informed consent form.

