Baseline labs including a comprehensive metabolic panel, lipid panel, and hemoglobin A1C will be assessed (unless labs within 3 months are available). Additional blood will be stored for future biomarker analysis. These blood samples will be stored in the Research commons freezer or the Winters Center freezers located in building 110 at the MEDVAMC. The biomarker analyses to be performed will be based on additional funding that will be obtained as the current grant that supports this study will not have adequate funds to run additional biomarkers. Hence while related to the study in that all the data from this study will be used, the funding is to be obtained in the future and the biomarkers to be decided in the future. Blood from only those who meet the troponin inclusion criteria and who are ultimately randomized to this study will be stored. The others will be discarded.

Randomization visit and titration of medications: After the pre-randomization visit, those individuals who meet the inclusion criteria including hs-cTnT levels, HF risk score will come for the randomization visit. A history (medical, surgical, social, family and medication history and review of systems) and physical examination will be performed, and the findings will be documented on the case report form. The physical examination

would include BP measurements (3 taken 2 minutes apart). Orthostatic BP measurements will be performed as well. We will use calibrated BP machines in the clinic for the purpose of the study. They will have a 2D and 3D echocardiogram with Doppler. Those with adequate images for cardiac strain assessment will then be randomized to one of the 3 groups. Randomization will be achieved with the help of the research pharmacy and ICTR (institute for clinical and translational research). Randomization will be stratified for age, presence of CHD, ACE-inhibitor/ARB use, and hs-cTnT levels greater than 14 ng/L. In addition to an echocardiogram, a carotid ultrasound and a pulse wave velocity assessment will be performed at the randomization visit

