Subjects randomized to the spironolactone group will be started at 25 mg daily, and titration up to 50 mg daily will be attempted (blood pressure, potassium levels permitting). Briefly, subjects will start taking their medication and 2 weeks later return for a brief visit when BP and potassium will be checked. If BP is greater than 125 mm Hg, spironolactone will be increased to 50 mg daily. Once maximum dose is achieved, serum potassium will be measured to ensure stability. For those randomized to spironolactone who have eGFR between 50 and 60 ml, medication will be started at 12.5 to 25 mg daily and then potassium, renal function measured at 2 weeks and 6 weeks and medication titrated based on results. In addition for those subjects with blood pressure on the lower side (120-130 mmHg systolic) or per principal investigators discretion spironolactone may be started at 12.5 mg daily for the first few days to ensure safety/ tolerability and then increased to 25 mg daily.

Subjects in the carvedilol group will similarly be started at 6.25 mg PO 2 times daily and titrated up to a maximum dose of 25 mg PO 2 times daily, again monitoring BP. Titration will be continued provided the systolic BP is >125 mm Hg. In addition for those subjects with blood pressure on the lower side (120-130 mmHg systolic) or per principal investigators discretion carvedilol may be started at 3.25 mg two times daily for the first few days to ensure safety/ tolerability and then increased to 6.25 mg two times daily.

Subjects in the usual-care group will continue receiving treatment from their primary care physician. However they will be required to come to the research clinics at baseline, 6 months, 12 months and at the end of study when history, physical, blood biomarker collection and imaging will be done similar to the carvedilol/ spironolactone treatment groups.

Visit 2: Subjects randomized to the spironolactone or carvedilol groups will come back for a 2-week visit, when they will have their BP checked and medications titrated if required. Those in the spironolactone arm will also have their serum potassium measured. As noted above for those on spironolactone and eGFR between 50-60 ml, potassium and renal function will be repeated at 6 weeks as well. Subjects may be called by the research coordinators approximately every 8 weeks for the first 6 months to enquire about tolerability and compliance. In addition this may help with subject retention.

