Visit 3: All subjects will return at 6 months. During the 6-month visit, all subjects will have a history and physical examination completed, and blood will be collected and part stored. Additionally, subjects will be interviewed about clinical events, including hospitalization, during the 6-month interval. Medication compliance will be assessed at this visit. Those on spironolactone will have their potassium checked

Visit 4: The 12 month visit will be identical to the 6 month visit

Visit 5: The final visit will capture details as in visit 3 and 4 but in addition also include all the imaging studies (echocardiogram, carotid ultrasound and pulse wave velocity measurement). Blood will be collected as well for biomarker assessment and additional samples stored for future research.

Subjects will be encouraged and requested to call/ notify us about any adverse events including side effects to medication, hospitalization, emergency room or urgent care visits. If there are any hospitalizations/ emergency room/ urgent care visits we will obtain information from the VA electronic medical record or from the hospital/ emergency room where they were cared for. There will be both paper and electronic data that will be nearly similar. The paper data will include the following HIPPA identifiers: name, date of birth, age, last four of the social security number, date of hospital admissions, date of discharge and any date of clinic visit during the duration of the study as well as participant address, phone number and email ID (if available). The electronic data stored at the VA will include name, last 4 of the social security number, date of birth, date of hospital admissions, date of discharge, any date of clinic visit and the research ID during the duration of the study. Electronic data stored in the BCM database which will be used for analysis will not have any HIPAA identifier and will include all other information. Data will be stored such that date of consent will be called "Day 0" and then other study events will be time stamped relative to the date of consent (example 6 month visit will be day 180 and so on). A date of birth will not be noted, but subject age will be recorded as this will be important in data analysis.

Sample Size/Data Analysis

Sample Size

How many subjects (or specimens, or charts) will be used in this study?

Local: 850 Worldwide: 850

Please indicate why you chose the sample size proposed:

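### A metabolic panel up to 3 months old may replace the baseline panel, and nothing clearly requires a newer eGFR before the first spironolactone dose

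*Combined protocol and SAP*

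**What the plan says.** All references are to the combined protocol and SAP.

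- **Exclusion Criteria, items 5 and 6:** "Renal insufficiency with eGFR less than 50 ml/min 6. Serum potassium greater than 5 meq/L". Neither item says how recent the value must be.
- **Procedure, Prerandomization Visit:** "During this visit, inclusion and exclusion criteria will be reviewed". On laboratory work for this visit: "Baseline labs including a comprehensive metabolic panel, lipid panel, and hemoglobin A1C will be assessed (unless labs within 3 months are available". The date from which the 3 months count is not given.
- **Randomization visit and titration of medications:** the visit consists of history, examination, blood pressure with orthostatic readings, and imaging. No chemistry is listed. "Randomization will be stratified for age, presence of CHD, ACE-inhibitor/ARB use, and hs-cTnT levels greater than 14 ng/L".
- **Spironolactone titration:** after starting, patients "2 weeks later return for a brief visit when BP and potassium will be checked". For reduced renal function: "For those randomized to spironolactone who have eGFR between 50 and 60 ml, medication will be started at 12.5 to 25 mg daily", with potassium and renal function at 2 and 6 weeks. Visit 2 repeats the later check: "for those on spironolactone and eGFR between 50-60 ml, potassium and renal function will be repeated at 6 weeks as well".
- **Visit 3 (6 months):** "Those on spironolactone will have their potassium checked".
- **Sample Collection, Blood:** 8 teaspoons are drawn at baseline. About 2 teaspoons, enough for a basic metabolic panel, are drawn after spironolactone is started, at titration and at 6 months.

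**The concern.** The discussion of medication risks under Potential Risks/Discomforts gives the exclusion of renal insufficiency, together with the low dose, as the reason hyperkalaemia should be uncommon. That exclusion protects patients only as far as the eGFR behind it is current. As written, a patient whose renal function has fallen below 50 since the chart value was taken could pass screening, be randomized and receive spironolactone. The same may be true of a patient whose potassium has since risen above 5. Because ACE-inhibitor/ARB use is a stratification factor, some patients will take spironolactone on top of one of these drugs. What is at stake is individual safety in the first weeks of treatment, not the validity of the comparison.

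**Working it through.** The plan states no figure to reproduce. The check has two parts: whether any section requires a newer value, and how old the value could be.

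**1. Is a newer value required before the first dose?**

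| Section | eGFR | Potassium |
|---|---|---|
| Exclusion items 5 and 6 | threshold, no window | threshold, no window |
| Prerandomization Visit | panel, or chart labs within 3 months | same |
| Exclusion item 17 (assessed at Visit 1) | liver tests only | liver tests only |
| Randomization visit | none listed | none listed |
| Titration, Visit 2 | weeks 2 and 6 if eGFR is 50 to 60 | week 2 for all on spironolactone |
| Potential Risks, Medications | none | after starting, and at study visits |
| Safety measures | none before dosing | before and 7 to 14 days after a dose change |
| Sample Collection, Blood | metabolic panel after starting | same; also refers to a chart result around the start |

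Every renal function measurement with a stated time, apart from the baseline panel, comes after the first dose. For potassium, the Safety measures and Sample Collection wording can be read to imply a value near the first dose if starting counts as a dose change. Neither says so outright.

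**2. How old could the eGFR be?**

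Inputs: 3 months taken as 90 to 92 days (assumption); hs-cTnT assayed weekly or every 2 weeks (Consent Procedures), so a wait of 0 to 14 days between the prerandomization visit and randomization; first dose on the day of randomization and no other delay (assumptions).

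- Window counted back from randomization: 90 to 92 days at first dose.
- Window counted back from the prerandomization visit: 90 + 0 = 90 days to 92 + 14 = 106 days.
- Sample taken at the prerandomization visit for everyone: 0 to 14 days.
- Fall in the maximum, randomization anchor: 90 − 14 = 76 to 92 − 14 = 78 days.
- Fall in the maximum, prerandomization anchor with a 14-day wait: (90 + 14) − 14 = 90 to (92 + 14) − 14 = 92 days.
- Overall, the maximum age falls by 76 to 92 days.

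The same range applies to potassium only if the ambiguous wording does not imply a value at the start.

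**3. Who is exposed?**

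The planned total is 205 to 210 in three equal groups, so the spironolactone arm is 205/3 = 68.3 to 210/3 = 70 patients. The documents give no rate at which eGFR or potassium crosses a threshold within 3 months, so no count of affected patients can be derived.

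**The case against.** The strongest reply is that the plan contains several safeguards. A full history, medication review and examination take place at the randomization visit. Exclusion item 19 lets the investigator keep out anyone at risk. Potassium supplements are stopped before the start, and a 12.5 mg start is allowed at discretion. Potassium is checked at week 2 under a dose-reduction and stopping algorithm, and a data safety monitoring board oversees the trial. Nothing in the documents shows that 3 months is too long for stable outpatients, and the day counts measure the age of a test, not harm. The data and safety monitoring form is a separate attachment that was not available and might add a rule. All of this is fair and keeps the point small. None of it clearly supplies a current eGFR before the first dose, and most of it acts only once the patient is exposed.

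Three stronger readings are tempting, and the documents do not support them:

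- **That no pre-dose potassium is taken.** The text is ambiguous, and ambiguity does not show that a check is missing.
- **That a patient whose eGFR has slipped from above 60 into 50 to 60 would miss the 6-week check and go without potassium until month 6.** The 6-week rule is not tied to the baseline value. The metabolic panel provided for after starting would normally include creatinine, so it would probably identify such a patient in time. Visit 2 itself names only potassium, so the sections are not perfectly aligned, but the effect is minor. The starting dose may not differ either, because 12.5 to 25 mg overlaps the usual 25 mg.
- **That the absence of a recheck date at potassium 5.0 to below 5.5 is part of this problem.** It affects every spironolactone patient with eGFR above 60, however fresh the baseline panel. It is a separate matter that the fix below does not address.

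**Conclusion.** The point holds in a narrow form. A chart panel up to 3 months old, with no stated anchor date, may decide the renal and potassium exclusions, and no section clearly requires a newer eGFR before spironolactone is started. A patient who currently meets exclusion 5, and possibly exclusion 6, could be given the drug, with the first scheduled chemistry about 2 weeks later. The oldest permitted eGFR at first dose is about 90 to 106 days, depending on the anchor and the assay wait, given same-day dosing and no other delay. The number of patients affected cannot be estimated from the documents. Power and type I error are unaffected. Severity is minor: this is a cheap improvement to patient safety. The conclusion would change if the monitoring form already requires a current panel.

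**What to change.** Amend the one sentence on baseline labs. Keep the 3-month allowance for the lipid panel and HbA1c only. Run potassium and creatinine/eGFR for every patient on the blood drawn at the prerandomization visit, and judge exclusions 5 and 6 and the eGFR 50 to 60 scheme on that sample.

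No extra visit is needed, because blood is already drawn then for hs-cTnT and NT-proBNP. The baseline draw is 8 teaspoons and a basic metabolic panel needs about 2. The cost is one routine panel for each patient who would otherwise have used chart labs. If the 850 given under Sample Size is the number screened (an assumption), 850 panels is the upper limit, and the added number is smaller because patients without recent chart labs already have one. Most of these panels will be for patients who never receive spironolactone. A few more screen failures should be expected. A lag of about 0 to 14 days to the first dose remains, longer if scheduling slips.
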